6.2 Methods and Timing for Assessing, Recording, and Analyzing Safety Parameters

Adverse Event (AE)

ICH E6 defines an AE as any untoward medical occurrence in a patient or clinical investigation volunteer administered a pharmaceutical product regardless of its causal relationship to the study treatment. An AE can therefore be any unfavorable and unintended sign (including an abnormal laboratory finding), symptom, or disease temporally associated with the use of medicinal (investigational) product. The occurrence of an AE may come to the attention of study personnel during study visits and interviews of a study recipient presenting for medical care, or upon review by a study monitor.

All AEs including local and systemic reactions not meeting the criteria for “serious adverse events” should be captured on the appropriate CRF. Information to be collected includes event description, time of onset, clinician’s assessment of severity, relationship to study product (assessed only by those with the training and authority to make a diagnosis, which would include MD, PA, Nurse Practitioner, DO, or DDS), and time of resolution/stabilization of the event. All AEs occurring while on study must be documented appropriately, AEs occurring within 7 days post vaccination determined to be related to the study product and/or 1 day post-blood donation and determined to be related to the procedure will be collected. All AEs will be followed to adequate resolution.

Any medical condition that is present at the time that the patient is screened should be considered as baseline and not reported as an AE. However, if it deteriorates at any time during the study, it should be recorded as an AE.

All AEs must be graded for severity and relationship to study product. FDA defines an AE as any untoward medical occurrence associated with the use of a drug in humans, whether or not considered drug related.

Severity of Event: The following guidelines will be used to quantify intensity.

Mild: events require minimal or no treatment and do not interfere with the patient’s daily activities.

Moderate: events result in a low level of inconvenience or concern with the therapeutic measures. Moderate events may cause some interference with functioning.

Severe: events interrupt a patient’s usual daily activity and may require systemic drug therapy

or other treatment. Severe events are usually incapacitating.

Life threatening: any adverse drug experience that places the patient or volunteer, in the view of the investigator, at immediate risk of death from the reaction as it occurred, ie, it does not include a reaction that had it occurred in a more severe form, might have caused death.

Changes in the severity of an AE should be documented to allow an assessment of the duration of the event at each level of intensity to be performed. Adverse events characterized as intermittent require documentation of onset and duration of each episode.

Relationship to Study Products: The clinician's assessment of an AE's relationship to vaccine is part of the documentation process, but it is not a factor in determining what is or is not reported in the study. If there is any doubt as to whether a clinical observation is an AE, the event should be reported. All AEs must have their relationship to study product assessed using the terms: related or not related. In a clinical study, the study product must always be suspect. To help assess, the following guidelines are used.

- **Related** – There is a reasonable possibility that the study product caused the adverse event. Reasonable possibility means that there is evidence to suggest a causal relationship between the study product and the adverse event.
- **Not Related** – There is **not** a reasonable possibility that the administration of the study product caused the event.

Serious Adverse Event (SAE)

An adverse event or suspected adverse reaction is considered "serious" if, in the view of either the investigator or sponsor, it results in any of the following outcomes:

- death,
- a life-threatening adverse event*,
- inpatient hospitalization or prolongation of existing hospitalization,
- a persistent or significant incapacity or substantial disruption of the ability to conduct normal life functions, or
- a congenital anomaly/birth defect.
- important medical events that may not result in death, be life-threatening, or require hospitalizations may be considered serious when, based upon appropriate medical judgment they may jeopardize the patient or volunteer and may require medical or surgical intervention to prevent one of the outcomes listed in this definition. Examples of such medical events include allergic bronchospasm requiring intensive treatment in an emergency room or at home, blood dyscrasias or convulsions that do not result in inpatient hospitalization, or the development of drug dependency or drug abuse.

* *Life-threatening adverse event. An adverse event is considered "life-threatening" if, in the view of either the investigator or sponsor, its occurrence places the patient or volunteer at immediate risk of death. It does not include an adverse event, had it occurred in a more severe form, might have caused death.*

All SAEs will be:

- recorded on the appropriate SAE CRF
- followed through resolution by a study clinician
- reviewed and evaluated by a study clinician

The SAEs must be reported as soon as the investigator becomes aware but within 5 working days for internal events, consistent with UMB policy. Investigators will report the SAE using the Adverse Event form in the Comprehensive Institutional Collaborative Evaluation of Research Online (CICERO) electronic system. The investigator will provide a summary of the problem or event in the text box labeled "adverse event information". The summary should include type or nature of the problem, a full description of the activities leading to the problem, interventions and/or actions taken in response, temporal relationship of event to the use of the investigational product/procedure and the current status of the participant. Additional information will be reported as it is received.

In the event of any serious adverse experience which, in the clinical investigator's opinion, justifies termination or modification of the study, it will be stopped and the IRB and ISM will be informed immediately. The IRB will be notified via CICERO, the IRB electronic tracking system.

Reactogenicity

Reactogenicity will not be measured in this study.

6.3 Reporting Procedures

AEs will be followed until resolution. Resolution of an AE is defined as the return to pretreatment status or stabilization of the condition with the expectation that it will remain chronic.

AEs and SAEs will be received, reviewed and managed by the ISM. The investigator is responsible for reporting events to VAERS according to the VAERS reporting criteria provided in the federal regulations. Regulatory Reporting of AEs that are determined to be vaccine related will be reported through the Vaccine Adverse Event Reporting System (VAERS).

6.4 Other Adverse Events (if applicable)

An unexpected AE is an adverse reaction, the nature or severity of which is not consistent with the applicable product information (e.g., package insert for the respective vaccine).

6.5 Reporting of Pregnancy

Although not AEs, pregnancies are reportable events (on the study-specific form) to the data management group. The pregnancy outcome will be reported if known including the health status of the mother and child including date of delivery and infant's gender and weight. If a volunteer's urine pregnancy test is positive prior to receiving the vaccination, they will be excluded from participating in the study.

Volunteers who are pregnant prior to receiving the vaccination will be excluded from participation in this study. Pregnancy will be reported as an unanticipated problem involving risk to research participants. Pregnancy will be reported to the UMB IRB within 5 working days of the time the research staff become aware of the pregnancy. In the event a volunteer becomes pregnant after

taking the vaccine the volunteer will be encouraged to complete all visits for safety follow up.

6.6 Type and Duration of Follow-up of Volunteers after Adverse Events

All SAEs will be followed until resolution even if this extends beyond the study-reporting period. Resolution of an AE is defined as the return to pretreatment status or stabilization of the condition with the expectation that it will remain chronic. The Clinical-PIs will follow all SAEs until resolution (return to pretreatment status or stabilization of the condition with the expectation that it will remain chronic) even if this extends beyond the study-reporting period.

At any time after completion of the study, if the investigator becomes aware of an SAE that is suspected to be related to study product, the investigator will report the event to the IRB.

6.7 Independent Safety Monitor

[name] will be the ISM for this clinical research study.

6.8 Oversight of Safety

The clinical investigators reserve the right to terminate this study should serious AEs or any other safety issue occur during the study. The UMB IRB upholds that all currently approved research that is not being conducted in accordance with the Human Research Protections Program and UMB IRB policies and procedures, Federal, State, and local requirements, or has been associated with unexpected serious harm to participants may be subject to suspension or termination. The IRB has the authority to suspend or terminate approval of research not being conducted in accordance with the IRB's requirements or that had been associated with unexpected serious harm to participants.

6.9 Clinical Monitoring/Site Monitoring Plan

The study will be monitored by the site clinical PIs. On a regular basis the clinical PIs will review patient charts/clinical reports, laboratory tests, outcomes, enrollment, procedure reports, and all adverse events. Site monitoring is conducted to ensure the human subject protection, study procedures, laboratory, study intervention administration and data collection processes are of high quality and meet sponsor, ICH E6, and other appropriate, regulatory guidelines and that the study is conducted in accordance with the protocol.

7 STATISTICAL CONSIDERATIONS

7.1 Study Hypothesis

This is an exploratory study rather than a hypothesis-driven study.

7.2 Sample Size Considerations

This study is exploratory in nature and is designed to identify associations among the presence and quantity of various intestinal bacteria, immune responses and clinical outcome. Thus it is designed to generate hypotheses but not to test any specific hypothesis based on prior data since no such data is available in the literature. The sample sizes planned for the study are therefore based on feasibility rather than power to reject any specific hypothesis. For large differences between groups the study will have good power to find statistically significant associations.

Data for withdrawn volunteers will be included in the intent to treat group. We anticipate a dropout rate of 20%. This is consistent with other studies of this nature performed at the University of Maryland.

7.3 Final Analysis Plan

The statistical analysis will depend on the hypothesis being evaluated. For example, if measuring cytokine levels, the level of cytokine, in pg/ml, will be obtained from extrapolation over standard curves. Seroconversion following challenge will be defined as a fourfold rise in serum Ab over pre-challenge levels. The geometric mean Ab level will be calculated for each time point and the peak time determined. The proportion of volunteers in each group who seroconvert will be determined for each antigen and Ab class at the peak time post-challenge. A positive ASC response will be defined for each immunoglobulin class and antigen as a post-vaccination count of at least 8 ASC/10⁶ PBMC that is ≥ 3 standard deviations above the mean pre-vaccination count for all volunteers in all cohorts combined. The proportion of volunteers in each group who develop each specific ASC response will be determined for each antigen and Ab class measured. The geometric mean ASC level at each time point and the peak post-immunization geometric mean will be calculated. Comparisons between systemic and local responses will be performed by using a two-sample t-test on log10 values or a Wilcoxon rank-sum test.

Comparisons between pre- and post-immunization levels within a single group will use a one-sample t-test on log10-transformed values or a Wilcoxon signed-rank test. Comparisons between two groups will use a two-sample t-test on log10 values or a Wilcoxon rank-sum test or the Kolmogorov-Smirnov test. Comparisons of proportions responding will use chi-square or exact tests. For comparisons among three or more groups, an overall analysis of variance or Kruskal-Wallis test will be done first; if that test indicates significant heterogeneity among groups, pairwise comparisons will then be made, with adjustment for the number of comparisons. Continuous immunological responses will be compared in the young adults and elderly by analysis of variance or Kruskal-Wallis test and pairwise comparisons as appropriate. Proportions of responders will be compared by chi-square or exact tests. Relationships between immunological measurements will be assessed using correlation analyses (for two continuous responses), t-tests (for comparing a continuous and a dichotomous response), and chi-square tests or exact tests (for comparing

two dichotomous responses). Two-sided p-values will be reported whenever two groups, or pre- and post-immunization levels within a group, are compared. $P < 0.05$ will be considered statistically significant. No imputation will be made for missing data.

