Population: Total of 200 healthy adults (ages 18 years or older) from the Baltimore-Washington metropolitan area and from the UMB campus

Number of 1

Sites:

Study indefinite

Duration:

Volunteer Up to 8 years

Participation

Duration:

Agent or Intervention: Licensed CVD 103-HgR oral *V. cholerae* O1 vaccine (Vaxchora®, PaxVax Inc., Redwood City, CA, USA)

Objectives:

1. To measure systemic and mucosal immune responses following immunization with the oral licensed cholera vaccine in consenting volunteers
2. To measure epigenetic changes which occur in response to vaccination with oral cholera vaccines
3. To integrate these multifaceted datasets into a systems biology approach to the understanding of the response to vaccination

Key Roles

Clinical PI [name], PhD
Assistant Professor of Pediatrics
Center for Vaccine Development
University of Maryland School of Medicine
[name]
[name]
Office [contact]
[contact]

Study Coordinator [name], CRNP
Center for Vaccine Development
University of Maryland School of Medicine
[name]
[name]
Office [contact]
[contact]

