1.2 Scientific Rationale

Immunological responses to *V. cholerae*

The immunological responses that correlate with protection from *V. cholerae* remain largely undefined or poorly defined. Thus, in depth studies of immune responses will be conducted with specimens from young adults and the elderly immunized with a single dose of CVD 103-HgR in this clinical research study. These studies should provide key insights into the characteristics and longevity of the immune responses that best correlate with protection from infection with *V. cholerae* and contribute to further our knowledge of the mechanisms underlying immunosenescence. Furthermore, these studies will enable a direct comparison of the magnitude and characteristics of the systemic and gut mucosa immune responses elicited by CVD 103-HgR immunization.

Summary

The specimens obtained in this clinical research study will be used to further our understanding of the protective immunological mechanisms that can be elicited systemically and may be applicable to other enteric pathogens.

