2 STUDY OBJECTIVES AND OUTCOME MEASURES

2.1 Objectives

1. To measure the systemic immune response following immunization with oral licensed cholera vaccine in consenting volunteers
2. To measure epigenetic change which occur in response to vaccination with oral cholera vaccine
3. To integrate these multifaceted datasets into a systems biology approach to the understanding of the response to vaccination

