2.2.2 Exploratory outcomes

The following brief descriptions provide some overview of the intended laboratory analyses to be performed with the specimens to be collected in this study. *This is not meant to be an exhaustive list of all the possible laboratory studies to be performed.*

1. Functional analysis of systemic (e.g., using serum, PBMC) anti-*V. cholerae* immune responses. These studies will include the following measurements, depending on specimen availability:
 - a. Ab levels to *V. cholerae* antigens in bodily fluids (e.g., serum, plasma)
 - b. Ab-secreting cells (ASC) to *V. cholerae* antigens
 - c. Cytokine production (e.g., intracellular IFN- γ , TNF- α , etc. by multichromatic flow cytometry or mass cytometry, IFN- γ production by Elispot and/or cytokine production in culture supernatants by multiplex technology.)
 - d. Memory (T_M) and B_M responses
 - e. CTL
 - f. innate immune responses (macrophages and dendritic cells)
2. Evaluation of homing characteristics of the various *V. cholerae*-responsive CD4+ and CD8+ T cell subsets
6. Study of TCR $\gamma\delta$ T cells and T_{reg} using multichromatic flow cytometry or mass cytometry using monoclonal antibodies to molecules that are characteristic of these cells (e.g., CD25 and FOXP3)
7. Measure the expression of host response genes to vaccination using functional genomics,

proteomics, and epigenetics

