3 STUDY DESIGN

This study is a single center, open label clinical research study to study the effect of oral immunization with the CVD 103-HgR cholera vaccine in younger adults and older adults (i.e., elderly). Healthy adults, ages 18 years to 64 years, will be recruited from the Baltimore-Washington area in response to campus flyers, advertising, and word-of-mouth. Study participants will receive the cholera vaccine. Subsequent to vaccination, small volume (up to 200 mL) or large volume (200 mL or greater) blood draws will be requested; the timing of these blood draws are not strictly set and the schedules in *Appendix D* and *E* are provided to give a general overview of the flow of research procedures. The timing of the blood draws and the types (small or large volume blood) is dependent on the research laboratory's needs. In general, more frequent scheduled blood draws will occur in the first year after vaccination and less often in the years after vaccination (up to 8 years of planned follow-up). Therefore, we intend to regularly re-screen for anemia and have set limits on the total volume of blood to be collected over any 56 day period.

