3.2 Interventions

Administration of licensed Live Oral Cholera Vaccine CVD 103-HgR. Participants will be given the vaccine, as packaged, and are to administer the vaccine as per the package insert. Briefly, approximately 100 mL of cool or room temperature purified bottled water is to be placed into a clean disposable cup. The contents of the buffer sachet are to be placed into the water and stirred. Then the contents of the active (lyophilized vaccine) sachet are to be placed into the water, then stirred for ~30 seconds. The reconstituted mixture should be completely ingested within 15 minutes. Illustrated instructions for the administration of CVD 103-HgR is presented in *Appendix E*.

Serial Blood Donor (small volume). After volunteers have been recruited, they may be contacted to have blood drawn, 1-20 times a year. No more than 2 $\frac{1}{3}$ cups (550 ml) will be taken over a 2-month period of time. The volunteer will be given a schedule of the dates when blood will be drawn and the amount of blood required each time they are contacted. At any time a donor may decline a blood specimen but choose to remain in the study. In most instances, 20 to 200 mL (4 to 40 teaspoons) will be collected at one visit. Visits for one-time or serial blood donations will take approximately ten minutes each and are performed at the Center for Vaccine

Development (CVD) Outpatient Research Clinic.

Blood Unit Donor (large volume). When large volumes of blood are desired, participants may be directed to the Greenebaum Cancer Center (GCC) Cell Component Therapy (CCT) Lab. Visits for the donation of a unit of blood/large volume (200- 500 mL) will take one hour. As part of the GCC CCT lab's standard operating procedure, a CBC will be performed on the day of donation (prior to donation of a unit of blood) for verification of a hemoglobin 12.5 or greater. If the hemoglobin is less than 12.5, the volunteer will be deferred and re-screened at a later date or they may have a smaller volume blood draw (\leq 200 mL) performed at the CVD Outpatient Research Clinic, if eligible by the hemoglobin criteria in *Appendix C*. Additional blood draws will take place according to the schedules attached.

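### Section 7.3 names independent-samples tests for systemic versus local responses that would most likely come from the same volunteers, and does not say what 'local' means

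*Combined protocol and SAP*

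**What the plan says.** Section 7.3 gives one method for this comparison: "Comparisons between systemic and local responses will be performed by using a two-sample t-test on log10 values or a Wilcoxon rank-sum test". It does not say which measure is local. The next paragraph of 7.3 handles pre- versus post-immunization levels within a group by a one-sample t-test on log10 values or a signed-rank test, so the plan already uses paired methods where both values belong to one volunteer.

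The scope statements differ. Objective 1 in the Protocol Summary is "To measure systemic and mucosal immune responses following immunization with the oral licensed cholera vaccine in consenting volunteers". Section 1.2 says the studies will enable a "direct comparison of the magnitude and characteristics of the systemic and gut mucosa immune responses elicited by CVD 103-HgR immunization". Section 2.1 gives Objective 1 as "To measure the systemic immune response following immunization with oral licensed cholera vaccine in consenting volunteers", with no mucosal part.

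On specimens, section 3 says: "Subsequent to vaccination, small volume (up to 200 mL) or large volume (200 mL or greater) blood draws will be requested". The research rows in Appendices A and B are PBMC, serum and gene expression, alongside CBC and screening laboratories. The only other specimen is urine for the pregnancy test. Section 2.2.2 lists antibody-secreting cells (ASC) and T-cell homing among its laboratory measures, and warns: "This is not meant to be an exhaustive list of all the possible laboratory studies to be performed".

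**The concern.** A two-sample or rank-sum test takes the two sets of values as coming from different people. Everyone in this study is to receive the vaccine, and no cohort is set aside for local measurements. If a systemic and a local value are both obtained, they would most likely come from the same volunteer. The standard error of the named test would then be wrong, in a direction that depends on the sign of the within-volunteer correlation.

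The test also rests on an undefined quantity. A reader of the Summary or of 1.2 expects mucosal data and a comparison with systemic data; a reader of 2.1 and the schedules expects blood and systemic responses only. At stake are missed differences in a study meant to generate hypotheses, and uncertainty about what the study sets out to measure.

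**Working it through.** **Is there a figure to reproduce?** No. Section 7.2 bases the sample size on feasibility and gives no effect size or power.

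**Inputs from the documents.** 200 volunteers (Protocol Summary); 20% dropout (7.2), so 200 × 0.8 = 160; two-sided 5% level (7.3). Using 160 pairs is a best case, because no number with a local measure is given.

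**Assumptions not in the documents.** Both values come from the same volunteers; equal variances on the log10 scale; correlation ρ from -0.2 to 0.7; a standardized difference d of 0.2, with larger values as a check.

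**Error.** With n pairs and common variance σ², the true variance of the mean difference is (2σ²/n)(1 − ρ). The two-sample test uses 2σ²/n. Its actual error is therefore 2·[1 − Φ(1.96/√(1 − ρ))]. For example, at ρ = 0.3, 1.96/√0.7 = 2.343, which gives 1.9%.

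**Power at a fixed difference.** With se = √(2/160) = 0.1118 and d = 0.2, d/se = 1.789.
- Two-sample: 1 − Φ((1.96 − 1.789)/√(1 − ρ)), the other tail being negligible for ρ above 0.
- Paired: Φ(1.789/√(1 − ρ) − 1.96), likewise.
- At ρ = 0 both tails are counted.

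| ρ | Actual error, two-sample | Power, two-sample | Power, paired |
|---|---|---|---|
| -0.2 | 7.4% | not compared (level not held) | not compared |
| 0 | 5.0% | 0.43 | 0.43 |
| 0.3 | 1.9% | 0.42 | 0.57 |
| 0.5 | 0.6% | 0.40 | 0.72 |
| 0.7 | 0.03% | 0.38 | 0.90 |

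**Simulation check, 160 pairs.** At ρ = -0.2, 0.3, 0.5 and 0.7 the two-sample t-test rejected a true null in 7.5%, 1.9%, 0.6% and 0.04% of 60,000 runs, and the paired t-test in 5.1%, 4.9%, 5.1% and 4.9%. In 20,000 runs the rank-sum test gave 7.4%, 2.0%, 0.7% and 0.09%, so choosing the named alternative does not help.

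**Other settings.** With 160 pairs and d = 0.5, both tests have power of at least 0.99. With 40 pairs and d = 0.5, at ρ of 0.3 to 0.7, the two-sample test has 0.63 to 0.69 and the paired test 0.76 to 0.98. If only half of the volunteers per measure give both values, ρ is replaced by 0.5ρ and the errors are 3.4%, 2.4% and 1.5% at ρ = 0.3, 0.5 and 0.7, and 6.2% at -0.2.

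**Scope.** Side by side, Summary Objective 1 and one sentence of 1.2 include mucosal responses. Section 2.1, sections 3 and 3.2, and both schedules are limited to systemic responses or to blood. No passage links the word 'local' in 7.3 to a specimen or assay.

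**The case against.** The strongest reply is that the test may never be run. If no local measure exists, the error rates are moot. The mucosal and local wording may simply be left over: the closing summary of 1.2 and section 3.4 speak of systemically elicited mechanisms, and section 7 has other wording that does not fit this study, such as seroconversion after challenge (7.3) and intestinal bacteria (7.2). Section 7.3 also opens by making the analysis depend on the hypothesis, so the test may not be fixed. All of this is fair. It lowers the weight of the point, but the sentence is still the only method named for this comparison, and leftover wording is a reason to remove it.

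A reader might infer that the mucosal objective has no specimen behind it at all. The documents do not support that. PBMC are scheduled, 2.2.2 lists ASC and T-cell homing, its list is declared open and its numbering jumps from 2 to 6, and CCR9 and CD103 appear among the abbreviations. A blood-based indirect measure is possible. What is missing is a statement that any such measure is the local response; a direct mucosal specimen is not scheduled.

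A reader might also infer that the named test invites false positives or loses most of its power. With positive correlation it is conservative; only negative correlation raises the error. At a fixed difference of 0.2 SD its own power hardly moves (0.43 to 0.38), and it is the paired test that gains. Section 7.2 claims good power only for large differences, where the loss is small.

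**Conclusion.** The point holds as a minor one. The 7.3 sentence needs changing either way: without a local measure the comparison cannot be made, and with one the named tests most likely ignore pairing. The size is an error of 1.9% to 0.03% in place of 5% at correlations of 0.3 to 0.7, with power of 0.42 to 0.38 against 0.57 to 0.90 at 0.2 SD and 160 pairs. At correlation -0.2 the error is 7.4%, and at zero there is no effect.

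These figures rest on shared volunteers, which is inferred, and on equal variances and correlations that the documents do not give. Partial overlap shrinks them. The mismatch between the Summary, 1.2 and 2.1 needs no such assumption. Section 7.1 declares the study exploratory, and the primary vibriocidal outcome in 2.2.1 is unaffected.

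A reader might infer that a more elaborate covariance model, or a comparison of gut-homing with non-homing cells, is needed. The documents do not establish a need for either.

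**What to change.** The sponsor should choose one of two routes.

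1. **Keep the comparison.** Replace the 7.3 sentence with: *Systemic and local responses measured in the same volunteers on a comparable log10 scale will be compared by a paired t-test on within-volunteer log10 differences or a Wilcoxon signed-rank test; two-sample tests will be used only for separate groups of volunteers.* State which measure is local, label a blood-based one as indirect, and align 2.1 with the Summary.
2. **Drop it.** If no local measure is intended, delete the 7.3 sentence, the words 'and mucosal' in Summary Objective 1 and the gut-mucosa comparison in 1.2, so that all match 2.1.

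Cost: route 1 needs a defined local measure, and a simple paired test drops volunteers with only one value. Some are likely, because the schedules vary, 7.3 plans no imputation, and section 3.2 allows that "At any time a donor may decline a blood specimen but choose to remain in the study". Route 2 is wording only, but it narrows the stated scope.
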